5.4. Screen Failures

Screen failures are defined as participants who consent to participate in the clinical study but are not subsequently randomly assigned to the study intervention. A minimal set of screen-failure information should be collected to ensure transparent reporting of screen-failure participants to meet the Consolidated Standards of Reporting Trials (CONSORT) publishing requirements and to respond to queries from regulatory authorities. Minimal information includes demography, screen failure details, eligibility criteria, and any SAE.

Individuals who do not meet the criteria for participation in this study (screen failure) may not be rescreened.

6. Study Intervention

Study intervention is defined as any investigational intervention(s), marketed product(s), placebo, or medical device(s) intended to be administered to a study participant according to the study protocol.

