6.6. Dose Modification

6.6.1. Tirzepatide

Tirzepatide is given once weekly by SC injection. There are no restrictions on the time of day each weekly dose of tirzepatide is given, but it is advisable to administer the SC injections on the same day of the week and similar time each week. If a dose of tirzepatide is missed, the participant should take it as soon as possible unless it is within 72 hours of the next dose, in which case, that dose should be skipped, and the next dose should be taken at the appropriate time.

Study drug dose modification is not permitted, except for:

- management of intolerable GI symptoms during the entire course of the study (see Section 6.6.2) and,
- management of participants with perceived excessive weight loss during the additional 2-year treatment period for participants with prediabetes at randomization only (see Section 6.6.3).

Only 1 dose reduction per participant will be permitted during the entire course of the study. All dose adjustments will be managed through IWRS.

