6.6.2. Management of Participants with Gastrointestinal Symptoms

Participants who experience intolerable GI symptoms (for example, nausea, vomiting, or diarrhea) at any time during the study, should first be counselled on dietary behaviors that may help mitigate nausea and vomiting, (for example, eating smaller meals, splitting 3 daily meals into 4 or more smaller ones, and stopping eating when they feel full). If symptoms persist, the participant should be prescribed, at the investigator's discretion, symptomatic medication (for example, antiemetic or antidiarrheal medication). A temporary interruption of study drug for 1 dose is permitted, provided the participant has taken the last 3 weekly doses. Study treatment should be resumed at the assigned dose immediately, either alone or in combination with symptomatic medication, which can also be utilized to manage symptoms (Section 10.9). Management of study drug after interruptions >1 dose is discussed in Section 7.1.1.

If intolerable GI symptoms (for example, nausea, vomiting, or diarrhea) persist despite the above measures, the investigator should contact Lilly to consider reinitiating study drug at the next-lowest maintenance dose in a blinded fashion (for example, 15 mg reduced to 10 mg, 10 mg reduced to 5 mg, or 5 mg reduced to placebo) (Section 10.9).

If intolerable GI symptoms persist despite symptomatic treatment, temporary drug interruption, and resumption at a lower dose of study drug, the participant should be discontinued from study drug. All participants who discontinue study drug should continue to attend scheduled study visits.

6.6.3. Management of Participants with Perceived Excessive Weight Loss During the Additional 2-year Treatment Period for Participants with Prediabetes at Randomization

As indicated in Section 5.3.1, if BMI ≤ 22 kg/m² is reached any time during the study, the recommended energy intake should be recalculated. From Visit 101 onwards, in the participants who have reached BMI ≤ 22 kg/m², if weight loss continues despite above measures and/or there are concerns related to degree of weight loss that may lead to discontinuation from study drug, the investigator should contact the Sponsor CRP to consider a study drug dose reduction in a blinded fashion (see Section 6.6.2 for details regarding study drug dose reduction).

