7.1.1. Temporary Study Drug Discontinuation

In certain situations, after randomization, the investigator may need to temporarily interrupt study drug. Every effort should be made by the investigator to maintain participants on study drug and to restart study drug after any temporary interruption, as soon as it is safe to do so. Distribution of study medication at the correct dose will be per IWRS instructions.

If study drug interruption is...	then...
2 consecutive doses or less	participant restarts study drug at last administered dose, as per escalation schedule.
3 consecutive doses or more	participant restarts study drug (at 5 mg, managed by IWRS) and repeats dose escalation scheme.
due to an AE	the event is to be documented and followed according to the procedures in Section 8.3 of this protocol.
due to intolerable persistent GI AE	participants should be treated as suggested in Section 6.6.2.

Abbreviations: AE = adverse event; GI = gastrointestinal; IWRS = interactive web response service.

Investigators should inform Lilly that study drug has been temporarily interrupted. The data related to temporary interruption of study treatment will be documented in source documents and entered on the eCRF.

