6.1. Populations for Analyses

For purposes of analyses, [Table GPHK.6.1](#) defines the analysis sets.

Table GPHK.6.1. Description of Analysis Datasets

Analysis Set	Description
Entered Participants	All participants who sign informed consent
Randomized Participants	All participants who are randomly assigned a study treatment
Modified Intent-to-Treat (mITT)	All randomly assigned participants who are exposed to at least 1 dose of study drug. Participants will be included in the treatment group they were randomized to.
Efficacy Analysis Set (EAS)	Data obtained during treatment period from mITT, excluding data after discontinuation of study drug (last dose date + 7 days).
Full Analysis Set (FAS)	Data obtained during treatment period from mITT, regardless of adherence to study drug.
Safety Analysis Set (SS)	Data obtained during the treatment period plus safety follow-up period from mITT, regardless of adherence to study drug.

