6.13.1.1. Analysis Related to the Efficacy Estimand

The analysis related to efficacy estimand will be conducted utilizing data in the EAS.

For the mean percent body weight change from randomization, a MMRM will be conducted. Restricted maximum likelihood (REML) will be used to obtain model parameter estimates and the Kenward-Roger option will be used to estimate the denominator degrees of freedom. The response variable of MMRM will be the percent change in body weight from baseline values obtained at each scheduled post baseline visit.

For the percentage of participants achieving at least 5% body weight reduction from randomization over time, a logistic regression model will be used with the response variable of the percentage of participants achieving at least 5% body weight reduction at each scheduled postbaseline visit.

For MMRM the independent variables of analysis model is treatment group, visit, treatment-by-visit interaction, stratification factors (prediabetes status at randomization, sex and country/pooled country) as fixed effects, and baseline body weight as a covariate. An unstructured covariance structure will model relationship of within-patient errors. If this model fails to converge, the following variance covariance structures will be tested in order until convergence is achieved:

- heterogeneous Toeplitz
- heterogeneous first order autoregressive
- heterogeneous compound symmetry
- Toeplitz
- first order autoregressive, and
- compound symmetry.

The first covariance structure that converges will be used.

With the aid of the MMRM analysis, 2-sided 95% CIs for mean percent change in body weight from randomization to the 72-week visit for tirzepatide 10 mg and 15 mg compared to placebo will be derived and summarized. The resulting least squares mean (LSM) estimates of mean percent change in body weight from baseline will be plotted by visit and by study treatment.

A logistic regression model with terms of treatment group, country/pooled country, sex, and prediabetes status at randomization as fixed effects, and baseline body weight as a covariate, will be conducted for percentage of participants achieving at least 5% body weight reduction from randomization at the 72 week visit. Missing body weight measurement at 72 week will be imputed by the predicted value from MMRM model aforementioned, then the continuous measurements will be dichotomized into status of achieving at least 5% body weight reduction

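### Under the efficacy estimand, the EAS keeps data collected on placebo injections as tirzepatide 5 mg data, but cuts the data of a 5 mg participant who stops injecting

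*SAP*

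**What the plan says.** SAP 6.1 (Table GPHK.6.1) and protocol 9.3 define the Efficacy Analysis Set (EAS) in the same way: treatment-period data from the mITT population, "excluding data after discontinuation of study drug (last dose date + 7 days"). SAP 6.13.1.1 ties the estimand to this set: "The analysis related to efficacy estimand will be conducted utilizing data in the EAS". SAP 6.2 defines the efficacy estimand as the effect if participants had stayed on their randomized treatment for the whole planned period. It also says that data are analyzed by randomized group, not by treatment received.

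For intolerable GI symptoms, protocol 6.6.2 lets the investigator and sponsor consider restarting study drug, blinded, one maintenance dose lower: "15 mg reduced to 10 mg, 10 mg reduced to 5 mg, or 5 mg reduced to placebo". Discontinuation is a separate, later step. It follows if symptoms persist despite symptomatic treatment, interruption and "resumption at a lower dose of study drug, the participant should be discontinued from study drug". Protocol 6.6.3 opens a second route to the same step: "From Visit 101 onwards, in the participants who have reached BMI" 22 or below. Protocol 6.6.1 adds: "Only 1 dose reduction per participant will be permitted during the entire course of the study".

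Placebo injections are study drug in this plan. Protocol 4.1.1.2.2 describes the first dose of study drug as tirzepatide or placebo. The mITT definition requires at least one dose of study drug, so it would contain no placebo arm on any other reading. The opening of protocol section 6 points the same way, although it defines the related term study intervention: "Study intervention is defined as any investigational intervention(s), marketed product(s), placebo, or medical device(s) intended to be administered to a study participant".

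**The concern.** Two 5 mg participants can both be off tirzepatide for the same reason and be handled in opposite ways. One stops injecting, and the data end 7 days after the last dose. The other receives placebo injections, the last-dose date keeps moving forward, and every later weight enters the model as a tirzepatide 5 mg observation. The second handling does not answer the question that the efficacy estimand asks.

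At stake is the 5 mg estimate that SAP 6.13 assigns to non-FDA regulators and publications. Within type 1 error control this means H5,1 (percent weight change and at least 5% reduction at Week 72). It also means, through the 5 mg third of the pool, the all-doses-combined Week 72 endpoints (SBP, triglycerides, non-HDL-C, HDL-C, fasting insulin) and time to T2DM. The uncontrolled 5 mg and all-doses-combined analyses on the EAS (SAP 4.3) share the issue.

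**Working it through.** **Tracing the rule**

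1. A move from 5 mg to placebo is a restart of study drug, not a discontinuation (protocol 6.6.2).
2. The EAS cut is triggered only by discontinuation of study drug (SAP 6.1), so it is not triggered here.
3. Analysis is by randomized group (SAP 6.2), so the data count as tirzepatide 5 mg.
4. Nothing in the SAP removes them. The intercurrent-event rules in SAP 6.13.1.3 are written for the hybrid estimand. Dose de-escalation appears only as an optional descriptive summary in SAP 6.11.2.
5. With one reduction allowed, only the 5 mg arm can reach placebo.
6. Up to Week 72 only the GI route applies. The other route starts at Visit 101 (Week 78) and needs BMI 22 or below, which from the minimum entry BMI of 27 is a loss of at least 1 − 22/27 = 18.5%.

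**Size**

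The plan gives no figure for this point and no switch rate. Assumption: f = 1% to 5% of the 5 mg arm (6 to 30 of 600). Inputs from protocol 9.2 are SD 10%, 25% dropout, an 11-point difference and 90% versus 25% responders (both stated for 10 and 15 mg), and annual T2DM hazards of 0.54% and 2.1%. The plan's own power statement reproduces: with 600 × 0.75 = 450 per arm, power for 11 points at 0.025 is about 1.00, against the stated more than 90%.

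- *H5,1 mean.* Dilution = f × effect lost. With 5 points lost (assumed) at f = 1%: 0.01 × 5 = 0.05. With 11 points lost (borrowed as an upper bound) at f = 5%: 0.05 × 11 = 0.55 percentage points. If half the effect is retained after the switch, these halve to 0.025 and 0.275. The standard error is 10 × √(2/450) = 0.667, so 0.55 is 0.83 of one standard error.
- *H5,1 responders.* Loss = f × (5 mg rate − 25%). At an assumed 60% rate: 0.35 to 1.75 points. At the borrowed 90%: 0.65 to 3.25 points.
- *All doses combined, Week 72.* Share of the pooled effect lost = f × r/(r + 2), where r is the 5 mg effect relative to 10/15 mg. For r = 0.5: 0.2% to 1.0%. For r = 1: 0.3% to 1.7%.
- *T2DM.* Worst case, switch at randomization: hazard ratio = [2 × 0.54 + (1 − f) × 0.54 + f × 2.1]/3/2.1. This gives 0.257 at f = 0, 0.260 at 1% and 0.270 at 5%.
- *H5,1 power.* An assumed 5-point effect diluted by 5% is 4.75 points, or 4.75/0.667 = 7.12 standard errors. Power is above 0.999 at alpha 0.025 and at 0.001. The testing figure is not shown, so alpha for H5,1 is assumed.

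**Comparing the two rules**

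Let E be the arm effect (5 to 11 points), and k the share of E that a switched participant would have had by staying on 5 mg. Assume no effect remains on placebo, and that cut data are in effect replaced by the arm mean. The error is −f·k·E under the current rule and +f·(1 − k)·E under the alternative.

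| k | Current rule | Cut at last active dose + 7 days |
|---|---|---|
| 1 | −0.05 to −0.55 | 0 |
| 0.5 | −0.025 to −0.275 | +0.025 to +0.275 |
| 0 | 0 | +0.05 to +0.55 |

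The MMRM also uses each participant's own on-drug weights, so the right-hand column is probably on the high side.

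**The case against.** The strongest reply is that every permitted step in protocol 6.6 belongs to the randomized regimen, so the EAS is right to keep the data. The SAP does not say so. That reading is also hard to hold where the step leaves no tirzepatide at all and the estimand is the effect of tirzepatide relative to placebo.

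A second reply is that the alternative cut is not clearly better. This is partly right: it is closer to the truth only if switched participants would have had more than half the arm effect on 5 mg, and the documents do not give that share. For participants switched because of marked weight loss, no effect is implausible. For those switched for GI intolerance the share is open.

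A third reply is that cutting only in a tirzepatide arm is asymmetric, because placebo participants on the same blinded pathway are kept. This fails: a placebo participant who steps down is still on randomized treatment.

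It also stands that the 1% to 5% range has no source, that the 0.55 combines three upper bounds, and that the protocol 10.9 flowchart, to which 6.6.2 refers, is not shown.

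A reader might infer something stronger: that all dose reductions and restarts contaminate the EAS, including the primary comparisons. The documents do not support that. Reductions from 15 to 10 mg and from 10 to 5 mg leave the participant on tirzepatide. After a longer interruption, the "participant restarts study drug (at 5 mg, managed by IWRS) and repeats dose escalation scheme" (protocol 7.1.1), so tirzepatide-arm participants return to drug. The estimand wording does not settle whether these reductions still count as randomized treatment, and the sponsor should reconcile that.

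**Conclusion.** The point holds as a minor one. The EAS wording departs from the efficacy estimand for one step, 5 mg to placebo. The text is clear on this; the size is not, because it rests wholly on an assumed switch rate. At 1% to 5% switching the 5 mg mean effect is diluted by at most about 0.05 to 0.55 percentage points, less if some effect is retained. The direction is toward placebo unless switched participants would have had no effect on 5 mg, in which case there is no dilution.

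It would be wrong to infer that a result is at risk. H5,1 keeps power above 0.999 under the stated assumptions. The 10 mg and 15 mg primary hypotheses cannot be touched, and the FAS/hybrid analyses for the FDA keep data regardless of adherence by design. The gain is one consistent rule for 5 mg participants who are off tirzepatide.

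**What to change.** In SAP 6.1, add that for a participant randomized to tirzepatide and switched to placebo, EAS data end at the last active dose plus 7 days, taken from IWRS records, while all data stay in the FAS. Report the current EAS rule as a sensitivity analysis, so that the two results bracket the answer under the error model above. Protocol 9.3 has the same wording. Under protocol 9.4.1 the change can be recorded in the SAP unless it is judged to alter a principal feature.

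The cost is a sentence or two and one repeat run of the affected EAS models, using dose adjustments already managed through IWRS. Trial conduct does not change. The downside is that slightly more 5 mg data are treated as missing at random, which may raise the 5 mg estimate. No view is taken on the dose-reduction rule itself.

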
To demonstrate that pooled tirzepatide 10 mg and 15 mg QW is superior to placebo for:
 
 • patient-reported outcomes (SF-36v2 acute form Physical Functioning domain score) 	
 • mean change in SF-36v2 acute form Physical Functioning domain score from randomization

Key Secondary (controlled for Type I error) at 72 weeks, pooled dose analysis
	

For tirzepatide QW (all doses combined), to demonstrate superiority to placebo for:
 
 • lipid parameters • SBP • insulin 	
 • mean change from randomization in 
 ○ triglycerides (mg/dL) ○ non-HDL cholesterol (mg/dL) ○ HDL cholesterol (mg/dL) • mean change in SBP (mmHg) from randomization • mean change in fasting insulin (pmol/L) from randomization

Key Secondary (controlled for Type I error) at 176 weeks, by dose analysis
	

For tirzepatide 10 mg and/or 15 mg QW doses, to demonstrate superiority to placebo (for participants with prediabetes at randomization) for:
 
 • body weight 	
 • mean percent change in body weight from randomization

Objectives	Endpoints

Key Secondary (controlled for Type I error) at 176 or 193 weeks, pooled dose analysis
	

For tirzepatide QW (all doses combined), to demonstrate superiority to placebo (for participants with prediabetes at randomization) in:
 
 • delayed progression to T2DM at 176 weeks • delayed progression to T2DM at 193 weeks 	
 • time to onset of T2DM during 176 weeks treatment period • time to onset of T2DM during entire study including safety follow up period

Additional secondary at 72 weeks, by dose analysis
	

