4.1.1.2.5. Safety Follow-up Period

Visit 801 or Visit 802

All participants are required to complete a safety follow-up visit (Visit 801 or Visit 802), according to the Schedule of Activities (Section 1.3). Participants discontinuing the study early and performing an ED visit will also be asked to perform the safety follow-up visit. During the safety follow-up period, participants will not receive study drug. Participants are also required to return any remaining study diaries to the study site at the end of this period.

For participants who discontinue or complete the study within the first 72 weeks, Visit 801 (safety follow-up visit) should be performed 4 weeks after the last treatment visit (Visit 21 or 99) or 4 weeks after the ED visit for those who decline to return for Visit 99. Participants with prediabetes continuing to Week 78 should not perform Visit 801.

For those participants without glycemic evidence of T2DM (Section 4.1.2.1), a 2-hour oral OGTT will be performed at Visit 802.

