6.2. General Considerations

Statistical analysis of this study will be the responsibility of Eli Lilly and Company (Lilly) or its designee. Some analyses and summaries described in this analysis plan may not be conducted if not warranted by data (for example, few events to justify conducting an analysis). Additional analyses of the data may be conducted as deemed appropriate.

Unless otherwise noted, tests of treatment effects will be conducted at a 2-sided alpha level of 0.05, and the confidence interval (CI) will be calculated at 95% 2-sided.

Unless specified otherwise, efficacy and safety will be assessed using the modified intention-to-treat (mITT) population, and data will be analyzed based on the randomized treatment (that is, not the actual treatment received by the participant). For submission of Study GPHK to the US Food and Drug Administration (FDA) to support the registration of tirzepatide for chronic weight management, the primary efficacy analysis will be conducted using Full Analysis Set (FAS). For other purposes, the efficacy analysis will be conducted using Efficacy Analysis Set (EAS). Safety analysis will be conducted using Safety Analysis Set (SS).

Summary descriptive statistics for continuous measures will include sample size, mean, standard deviation (SD), median, minimum, and maximum. The analysis model to make comparisons among treatment groups relative to continuous measurements assessed over time will be either analysis of covariance (ANCOVA) or a mixed model for repeated measures (MMRM).

Kaplan-Meier method will be used for estimation of cumulative event-free survival rates over time, and Cox proportional hazards regression analysis will be used to compare hazards rates among treatments.

Summary statistics for categorical measures (including categorized continuous measures) will include sample size, frequency, and percentages. Logistic regression will be used to examine the treatment difference in binary efficacy outcomes if there is a need to adjust for covariate. Otherwise, Fisher’s exact test will be used to examine the treatment difference.

Summary statistics for discrete count measures will include sample size, mean, SD, median, minimum, and maximum.

Unless specified otherwise, baseline will be defined as the last available non-missing measurement during Visit 1 to Visit 3. For the safety related parameters, the definition of baseline and postbaseline are specified in [Table GPHK.6.2](#).

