6.13. Efficacy Analyses

For submission of Study GPHK to the US FDA to support the registration of tirzepatide for chronic weight management, all primary and key secondary efficacy assessments will be guided by the “hybrid” estimand conducted using the FAS. Assessment of the primary and key secondary objectives (except for endpoint “delaying the onset of diabetes during 176 weeks or 193 weeks [for participants with prediabetes at randomization]”) will be conducted with multiple imputation of missing data (see Section 6.13.1.3).

For other regulatory agencies, publications and other purposes, the assessment of efficacy objectives will be guided by the “efficacy” estimand using the EAS.

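### The 193-week diabetes endpoint is assigned to analysis sets that exclude the off-drug follow-up it is defined to include

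*SAP*

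**What the plan says.** Protocol Section 3 lists two type-I-error-controlled diabetes endpoints for participants with prediabetes. The first is onset during the 176-week treatment period (H_p,14). The second is "time to onset of T2DM during entire study including safety follow up period" (H_p,15). Protocol Section 4.1.1.2.5 makes the follow-up a separate period: "During the safety follow-up period, participants will not receive study drug". The Schedule of Activities (Protocol Section 1.3.2) places an OGTT and HbA1c at Visit 802, 17 weeks after treatment.

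SAP Section 6.13 fixes the analysis sets. For the FDA submission, "all primary and key secondary efficacy assessments will be guided by the" hybrid estimand, on the Full Analysis Set (FAS). "For other regulatory agencies, publications and other purposes, the assessment of efficacy objectives will be guided by the" efficacy estimand, on the Efficacy Analysis Set (EAS). The same section names the 176- and 193-week diabetes endpoint as an exception, but only from multiple imputation.

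SAP Table GPHK.6.1 then defines the sets:

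- FAS: "Data obtained during treatment period from mITT, regardless of adherence to study drug".
- EAS: treatment-period data, "excluding data after discontinuation of study drug (last dose date + 7 days").
- Safety Analysis Set (SS): "Data obtained during the treatment period plus safety follow-up period from mITT, regardless of adherence to study drug".

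SAP Section 6.2 gives the SS its use: "Safety analysis will be conducted using Safety Analysis Set (SS"). The Cox-model row for both diabetes endpoints in SAP Table GPHK.6.4 names no other set and no censoring time.

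**The concern.** H_p,15 differs from H_p,14 only in weeks 176 to 193, and neither efficacy set contains data from those weeks. An analyst who follows the set definitions would discard the Visit 802 glycemic results. An analyst who follows the endpoint name would keep them. Both could claim to be following the SAP, and they would report different confirmatory estimates.

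What is at stake is what a 193-week result means. On the stated sets it cannot show diabetes that emerges after planned drug cessation in participants who completed treatment. Protocol Section 10.12 records that the follow-up was lengthened to 17 weeks to describe glycemic status better, so the sets leave out the weeks added for that purpose.

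The efficacy estimand has a further conflict: SAP Section 6.2 states it at 176/193 weeks, but its data set stops with the treatment period. SAP Section 6.14 has the only censoring rule in the SAP, and that rule is for selected safety parameters.

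**Working it through.** **Consistency of the text**

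1. 176 + 17 = 193, so the added window is exactly the safety follow-up.
2. Table GPHK.6.1 separates the treatment period from the treatment period plus safety follow-up. The shorter phrase therefore cannot be read as covering both.
3. Section 6.13 singles out this endpoint for an exception and does not extend that exception to the analysis set.
4. Hence FAS and EAS data end with the treatment period. For a participant who completes 176 weeks, H_p,15 and H_p,14 use the same data.

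**The plan's own power figure**

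Protocol Section 9.2 gives more than 90% power for the diabetes comparison. With its annual hazards (0.54% and 2.1%), 22% annual dropout and 1,080 versus 360 participants, Schoenfeld's formula gives 88.5% at 3 years and 90.8% at 176 weeks. A simulated log-rank test gives 95.0% and 95.8%. The stated power reproduces to within 2 points and is not in dispute.

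**Illustrative size**

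Inputs from Protocol Section 9.2: 2,400 × 60% = 1,440 with prediabetes, split 3:1 into n = 1,080 (tirzepatide, pooled) and 360 (placebo); hazards h = 0.0054 and 0.021 per year; 49% dropout over 3 years. Dropout is treated here as censoring when the participant leaves treatment.

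- Dropout hazard: d = −ln(0.51)/3 = 0.2244 per year.
- Treatment: T = 176 weeks = 3.373 years. Washout: w = 17 weeks = 0.326 years.
- On-treatment events = n·h/(h+d)·(1 − exp(−(h+d)T)): 13.7 tirzepatide, 17.3 placebo.
- On-treatment person-years = events/h: 2,535 and 826.
- Event-free at Week 176 = n·exp(−(h+d)T): 497 and 157, together about 655.
- Washout events = number event-free × (1 − exp(−h_off·w)). Placebo stays at 2.1% per year: 1.1 events.
- Washout person-years: about 162 and 51, together 213.
- Hazard ratio = ratio of events per person-year. Wald z = −ln(HR)/√(1/e₁ + 1/e₂), where e₁ and e₂ are the total events in the two arms.

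The tirzepatide hazard after stopping, h_off, is not in the documents, so it is varied:

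| h_off per year (assumption) | Washout events, tirzepatide | Total events, tirzepatide vs placebo | HR | Wald z |
|---|---|---|---|---|
| Follow-up excluded | none | 13.7 vs 17.3 | 0.26 | 3.8 |
| 0.54% (on-drug level) | 0.9 | 14.6 vs 18.4 | 0.26 | 3.9 |
| 1.32% (midway) | 2.1 | 15.8 vs 18.4 | 0.28 | 3.7 |
| 2.1% (placebo level) | 3.4 | 17.1 vs 18.4 | 0.30 | 3.6 |
| 3.15% (1.5 × placebo) | 5.1 | 18.8 vs 18.4 | 0.33 | 3.4 |

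With Schoenfeld's variance, z = −ln(HR)·√(total events × 0.75 × 0.25), which runs from 2.9 to 3.4. Every case exceeds 1.96.

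Sensitivity: with hazards derived from the 3-year risks of 1.6% and 6%, the placebo-level case moves the HR from 0.261 to 0.305. With a 3-year treatment horizon it moves from 0.257 to 0.309.

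**The case against.** The best defence is that the intent is plain. The endpoint definition, the estimand wording at 176/193 weeks, Table GPHK.6.4 and the hypothesis list all point to a window that includes follow-up. A specific endpoint would normally be read as overriding a generic table of sets, and the literal reading makes H_p,15 nearly a duplicate of H_p,14. SAP Section 6.2 also drops only data recorded after the end of study participation, which it defines to include the follow-up visit. Visit 802 data are collected in any case, and the expected difference is a handful of events.

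Intent is indeed clear, which is why this is a contradiction and not a missing design element. But nothing in either document says that the endpoint overrides Table GPHK.6.1, and the Section 6.2 rule is only an outer limit on usable data.

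Several limiting points stand:

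- Whether the EAS cut at last dose plus 7 days applies to someone who finished the planned treatment is arguable. The treatment-period limit excludes the follow-up either way.
- The 17 weeks are 17/193 = 8.8% of a completer's calendar time, but only 213/(3,360 + 213) = 6.0% of the modelled person-time.
- The illustration covers on-treatment data plus completers' washout. It leaves out the 17-week follow-up of those who stop after Week 72, and it is not a figure for the hybrid analysis, which would need retention assumptions that Protocol Section 9.2 does not give.
- The FAS does keep off-drug data from early discontinuers within the treatment period, such as the Visit 199 OGTT.
- The absent censoring sentence would, taken alone, be only a missing detail.

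**Conclusion.** The concern holds. As written, the SAP analyses a type-I-error-controlled endpoint on data sets that exclude the weeks separating it from its 176-week counterpart. Under the planning assumptions, about 655 of 1,440 participants would have their washout ignored. The likely numerical effect is modest: no change in the hazard ratio of 0.26 if the off-drug hazard stays at the on-drug level, 0.30 if it reaches the placebo level, and 0.33 at 1.5 times placebo. Those values rest on constant hazards, dropout treated as censoring, and an off-drug hazard that is assumed. The expected test outcome does not change; the estimate and its interpretation may. It should be corrected before the final database lock, because a limited group has access to unblinded data from the primary lock (Protocol Section 9.5) and the data scope should not be left to be chosen afterwards.

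**What to change.** Amend SAP Sections 6.1 and 6.13 and Table GPHK.6.4, and align the matching set definitions in Protocol Section 9.3:

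1. For the hybrid estimand, analyse H_p,15 on data from treated (mITT) participants with prediabetes through the end of safety follow-up, using either the SS data scope or a newly named efficacy set.
2. State separate cut-off and censoring times: Week 176 for H_p,14, and end of study participation as defined in SAP Section 6.2 for H_p,15.
3. State how the efficacy estimand treats the planned off-drug weeks. One option is EAS data plus the planned follow-up of participants who completed 176 weeks on drug. The documents do not settle this, so the sponsor must choose and record it.

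The cost is wording only, because the Visit 802 OGTT and HbA1c are already scheduled. The one disadvantage to the sponsor is that the 193-week hazard ratio may be less favourable.
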